There are limited reports of 5FU specifically for treatment of anal lesions. In one study evaluating treatment of patients with perianal HSIL, 7 of 8 patients treated with topical 5FU cream applied twice weekly for 16 weeks had no evidence of Bowen's disease on follow-up biopsies at 12 months post-treatment (17). An open-label study has been reported in 46 patients; multifocal lesions were seen in 76% and 74% had anal HSIL. All were HIV-positive. In this study, 1 g of 5-fluorouracil 5% was inserted using an applicator twice weekly at night for 16 weeks. Complete responses were seen in 12 of 34 patients with anal HSIL and partial responses with a decrease in HSIL to LSIL were seen in an additional eight subjects. Moderate to severe side effects were reported in 48% (18). Results were recently reported in a study of 11 patients using a slightly different schedule in which approximately 0.25 g of 5FU was placed intra-anally at bedtime for a median treatment time of 20 weeks. One patient discontinued therapy due to side effects and 73% of patients experienced some amount of irritation. Six patients had improvement in their disease including one with extensive condyloma who had no lesions on follow-up HRA (19). Jay et al. (20) described the results of a trial from the University of California San Francisco (UCSF) Anal Neoplasia Clinic using intra-anal 5FU twice daily for five days, followed by a nine-day rest period. The cycle was repeated four times and patients re-evaluated. Twenty patients with extensive anal HSIL involving more than 75% of the circumference were evaluable. Complete histologic regression was seen in three, no response in one, and 16 had a significant decrease in volume of disease to 25-50% that allowed in-office ablation using infrared coagulation. Subjects experienced pain, ulceration, bleeding, and exacerbation of herpes simplex. However, only two of the entire group of 27 discontinued treatment because of side effects, and four were considered non-compliant and not evaluable because they completed less than two cycles (20).

While these results are difficult to compare due to differences in treatment protocols, all the studies suggest that anal HSIL may resolve or improve with topical 5FU therapy.

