## 5.4 Criteria for Discontinuing Study Treatment

The investigator should discontinue the study treatment if there is evidence of Grade 4 AEs at least possibly due to study treatment.

The investigator may discontinue study treatment, at his or her discretion, if the participant experiences Grade 3 AEs at least possibly due to study treatment. Alternatively, study treatment may be held and dose reduced as described in [Section 5.3](#).

Participants who prematurely discontinue treatment should remain in study follow-up according to the schedule of events. If treatment is discontinued prior to Week 16, then the participant should undergo HRA with biopsies for the primary endpoint at Week 20. Off-study treatment for anal HSIL prior to Week 20, other than randomized treatment, should be avoided.

Similarly, participants who prematurely discontinue study treatment administered beginning at Week 24 should undergo HRA with biopsies at Week 44.

Participants should discontinue assigned study treatment (or observation without treatment) if progression of disease is suspected. For example, the pathologist suspects possible superficial invasion or there is worsening of histology, as evidenced by an

endophytic growth pattern and pushing borders, or if the clinician notes suspicious friability, ulceration, mass effect, heaped-up borders, and/or markedly abnormal vascular pattern on HRA. These participants should remain in study follow-up and receive treatment as determined by the site investigator.

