#### 6.1.1 Complete medical history

To include

- Duration of HIV and AIDS diagnoses, history of opportunistic illnesses, and date of initial diagnosis of anal HSIL. If at all possible, the investigator should obtain a copy of the pathology report from the first diagnosis of anal HSIL.
- CDC HIV risk categories and history of AIDS defining conditions.
- Current medications (as required by [Section 5.2](#)) and history of drug allergies.
- All antiretroviral medications taken within the past 30 days will be documented. Current pain medication usage will be quantified.
- Concurrent anal problems including condyloma, hemorrhoids, fissure, skin tag, fistula, sexually transmitted infections, bleeding, pruritus, and pain or irritation.
- Prior treatments of anal HSIL and condyloma.
- T-cell nadir: The participant's prior nadir CD4+ cell count (absolute value and date) must be documented, when possible, with a copy of the nadir CD4+ cell count report and entered on the CRF. If this documentation is not available, then participant recollection of nadir CD4 will suffice. For participants who do not know the exact nadir value and for whom there is no source documentation, then recall of the categorical nadir (e.g., <50, <100, <200 cells/mm^3) and year will suffice.

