## 6.12 Early Treatment Discontinuation Visit

- Clinical assessment: The participant's medical history will be updated for any changes. A review of systems for any new or changed local symptoms, such as hematochezia, dyschezia, erythema, swelling, or pruritus. A targeted physical exam should be performed as indicated (see [Section 6.2.1](#)).
- Anal swab for HPV testing.
- Anal cytology (standard of care) and anal swab for HPV testing.
- HRA exam of the anal canal. The number of involved octants, location, and percent circumference of HSIL will be documented per [Section 9.1](#).
- All participants should have biopsies obtained as per [Appendix V](#). Please note that pathologists should remain blinded to the treatment assignment.
- Any HSIL diagnosed at this visit should be treated off study at the discretion of the treating provider.
- All lesions, all aspects of the anal transformation zone, distal canal and perianus will be photographically documented.
- Collect the treatment diary and evaluate adherence. All containers of study treatment should be collected. Partially used containers should be weighed to measure the amount of cream used.
- AMC-088 Smoking Status and Recent Sexual History Questionnaire: A review of smoking and recent sexual behavior.

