### **9.1    Definition of Clinical Response (by Subject)**

- 9.1.1    Complete Response (CR): The absence of HSIL histology for all biopsies and the absence of HSIL cytology.
- 9.1.2    Partial Response (PR): 1) The regression of HSIL histology but HSIL cytology is present, or 2) Reduction in number of octants with HSIL.
- 9.1.3    No Response: The presence of HSIL histology with no change in the number of octants with HSIL with or without HSIL cytology.
- 9.1.4    Spontaneous Regression: The absence of HSIL histology and HSIL cytology following no treatment.

Please note that LSIL is treated the same as no SILs for the purpose of these definitions. For example, a participant with all biopsies showing LSIL and cytology showing LSIL would be considered a CR.

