### 10.7 Primary Analyses

The primary analysis population for efficacy and safety is an intent-to-treat (ITT) population, which consists of all participants who are randomized to 5-fluorouracil 5% or observation. The proportion of participants achieving complete response in the 5-fluorouracil 5%, and the proportion of participants with spontaneous regression in the observation arm will be calculated as the number achieving complete response or experiencing spontaneous regression through the primary endpoint visit (Week 20) divided by the number in the intent-to-treat population. For the treatment comparison (topical 5-

fluorouracil 5% vs. observation) the proportions will be compared across sites using stratified Mantel-Haenszel-Cochran tests at the one-sided 0.05 alpha level. This means that participants who drop out or do not provide evaluable data contribute to the analysis since they are included in the denominator, i.e., they are essentially treated as failures.

Since the imiquimod arm was stopped early, we will describe comparisons between imiquimod and observation using only the participants randomized to imiquimod and observation prior to closure of the imiquimod arm. As a secondary objective, imiquimod 2.5% and topical 5-fluorouracil 5% will be compared using a stratified Mantel-Haenszel-Cochran test at the two-sided 0.05 alpha level using participants randomized prior to the closure of the imiquimod arm.

The primary endpoint will include intra-anal HSIL present on cytology or histology. Perianal HSIL will be descriptively reported separately, as well as combined with the primary endpoint. In addition to the primary intent-to-treat analysis (which includes all randomized participants), we will perform a sensitivity analysis that treats participants who receive HSIL treatment other than randomized treatment (or observation participants that receive any treatment) prior to Week 20 as failures; participants who are lost to follow-up or inevaluable are also still treated as failures. We will also perform a per-protocol analysis using the subset of participants who were adherent to the protocol.

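### Section 6.12 tells sites to treat HSIL found at early discontinuation with no time limit, against Section 5.4's instruction to hold off-study treatment until the Week 20 primary-endpoint biopsies

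*Combined protocol and SAP*

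**What the plan says.** Section 6.12 (Early Treatment Discontinuation Visit) calls for HRA, biopsies and cytology, and then instructs: "Any HSIL diagnosed at this visit should be treated off study at the discretion of the treating provider". No week is named, and there is no reference to Section 5.4.

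Section 5.4 (Criteria for Discontinuing Study Treatment) deals with the same participants. They stay in follow-up, and "If treatment is discontinued prior to Week 16, then the participant should undergo HRA with biopsies for the primary endpoint at Week 20". It adds: "Off-study treatment for anal HSIL prior to Week 20, other than randomized treatment, should be avoided". The exception is suspected progression, where the site investigator decides on treatment.

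Section 9.1 defines complete response as "The absence of HSIL histology for all biopsies and the absence of HSIL cytology", with no condition about other treatment received.

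Section 10.7 makes the intent-to-treat comparison primary. It then says "we will perform a sensitivity analysis that treats participants who receive HSIL treatment other than randomized treatment" before Week 20 as failures, and "We will also perform a per-protocol analysis using the subset of participants who were adherent to the protocol".

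**The concern.** A participant who stops 5FU early and has biopsy-proven HSIL at the discontinuation visit is covered by both instructions. Section 6.12 says the HSIL should be treated. Section 5.4 says treatment should wait until the Week 20 biopsies have been taken. A coordinator working from the visit section would see only the first.

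The Week 20 biopsies are the primary endpoint. If ablation clears the lesions before then, the biopsies and cytology can be negative and the participant meets the complete response definition. The primary analysis would then credit 5FU with a clearance produced by another treatment.

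The exposure is lopsided. Participants on observation have no topical treatment to stop, and 5.4 ends observation only for suspected progression, where treatment is already allowed. Any miscrediting through 6.12 would therefore mainly favour 5FU.

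**Working it through.** **Side-by-side reading.** No figure in the plan is at issue, so the check begins with the text.

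1. HSIL can be diagnosed at the 6.12 visit before Week 20. Everyone enters with biopsy-proven HSIL (Section 3.1.2), and biopsies are taken at that visit.
2. The 6.12 sentence also appears in Section 6.11 (Week 44), where it is harmless because that is the last visit. Section 6.6 places off-study treatment of residual HSIL at the Week 20 visit, in line with 5.4. Only in 6.12 can the sentence apply before the primary endpoint.
3. The 5.4 exception covers suspected progression, not any HSIL.
4. The complete response definition does not exclude other treatment. Section 10.7 applies the failure rule in a sensitivity analysis, which implies that the primary analysis does not.

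**Effect per person.** With 35 per arm (Section 10.3), one miscredited participant adds 1/35 = 2.9 points to the 5FU response rate.

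**Illustration over the whole trial.** The plan states no early-stopping rate. Assumptions:

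- Stopping: Section 1.1.1 describes a trial of the same 5-days-on, 9-days-off schedule over four cycles, in which "only two of the entire group of 27 discontinued treatment because of side effects". This gives 2/27 = 7.4%. If the same rate holds for each four cycles, eight cycles give 1 − (25/27)² = 14.3%.
- Clearance: 39% to 50%, the electrocautery results in Section 1.2 (39% intent-to-treat for all SIL, 50% per protocol for HSIL, both with monthly treatment).
- Every stopper has HSIL and is ablated before Week 20.

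| Stopping rate | Stoppers among 35 | Miscredited at 39% | Miscredited at 50% |
|---|---|---|---|
| 7.4% | 2.6 | 1.0 (2.9 points) | 1.3 (3.7 points) |
| 14.3% | 5.0 | 1.9 (5.6 points) | 2.5 (7.1 points) |

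The exact 95% interval for 2/27 is 0.9% to 24.3%, or 0.3 to 8.5 stoppers among 35.

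**Effect on the test, same assumptions.** Suppose 5FU does nothing, so that response is 10% in both arms. Exact enumeration of the pooled two-proportion z test (35 per arm, final bound 1.955 from Table 10-A, unstratified, ignoring the interim look) rejects with probability 0.029. With 7.4% stopping, the 5FU rate becomes 0.926 × 0.10 + 0.074 × c for clearance c. Rejection is then 0.052 at c = 0.39 and 0.063 at c = 0.50.

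**Who a wording change could still reach.** The current version is dated 02AUG2023, enrolment closed on 01JUL2023 (Section 1.2), and recent accrual was about one per month (Section 10.1).

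- Sixteen weeks before 02AUG2023 is 12APR2023. From then to 01JUL2023 is 80 days, about 2.6 participants, or 1.3 on 5FU.
- Their remaining treatment time runs from 0 to 80/7 = 11.4 weeks, on average 5.7 of 16.
- With a constant hazard, expected new stoppers on 5FU are 1.3 × [1 − (1 − 0.074)^(5.7/16)] = 0.04, or 0.07 with 14.3% in place of 7.4%.
- Someone who had already stopped but not yet reached Week 20 could add slightly to this.
- On schedule, the last participant finishes treatment by 21OCT2023, and the Week 20 window (+21 days) closes by 09DEC2023.

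**The case against.** The strongest reply is that both instructions can be followed. Section 6.12 says where treatment happens and leaves it to the provider's discretion, while 5.4 is the specific rule on timing. Section 6.12 also serves participants who stop cross-over 5FU after Week 24, for whom no Week 20 limit applies; that may be why no week is named. A site that reads both sections would defer. This reading is possible, but 6.12 says HSIL should be treated, does not ask for deferral, and does not direct the reader to 5.4.

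The second reply is that the analysis already foresees such treatment, and that leaving the failure rule out of the primary intent-to-treat analysis is a recognised choice. This stands in part. The sensitivity and per-protocol analyses would help to show the effect, but they do not change the primary result.

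The third reply is that the numbers are soft and that little can still be changed. This stands. A reader might take 7.1 points as an upper bound. It is not: 8.5 stoppers at 50% clearance would give 8.5 × 0.50 / 35 = 12.1 points. Nor is the range a best estimate, since it supposes that every site disregards 5.4 and that clearance before Week 20 matches repeated monthly electrocautery. The 64–81% for infrared coagulation in Section 1.1 is a per-lesion figure. The same section reports HSIL at other untreated sites in up to 70% of patients, so it should not be used as a rate per participant.

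**Conclusion.** The conflict is real and sits in current protocol text. If 6.12 is followed before Week 20, the primary analysis can credit 5FU with a clearance achieved by ablation, at 2.9 points per participant. How many participants this involves is unknown and probably small. The 2.9 to 7.1 point range and the rejection probabilities are illustrations under strong assumptions (the borrowed stopping rate, ablation of every stopper, and electrocautery clearance). For new stoppers after 02AUG2023, the expected number on 5FU is below 0.1. The point is minor.

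Two stronger readings are not supported. A reader might infer that the 5FU result is biased, but nothing in the documents shows that any participant was treated in this way. A reader might also infer that the 10.7 sensitivity analysis cannot be run because treatment dates are missing. Section 6.1.1 lists "Prior treatments of anal HSIL and condyloma" in the medical history, and the history is updated at visits. The text does not say that a date is recorded, but the case report forms are not among the documents. Date capture is a point to confirm, not a shown gap.

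**What to change.** Keep the 6.12 bullet and add: *For participants who discontinue initial randomized treatment before Week 20, defer this treatment until after the Week 20 HRA and biopsies unless progression is suspected (Section 5.4).* This preserves the progression exception and leaves the bullet unchanged for those who stop cross-over 5FU after Week 24.

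Section 11.2 requires CTEP and IRB approval for an amendment, so the sentence is best carried in the next one. Given how few participants remain on treatment, remind sites of 5.4 now.

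Also confirm that the type and date of any off-study HSIL treatment before Week 20 are on record for all early discontinuers, including those already past Week 20, because the planned sensitivity analysis relies on them. The cost is one sentence, one message to sites and a record check. No new visit or procedure is needed.

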## **7.0 ADVERSE EVENT REPORTING**

CTEP Version 5.0 of the NCI Common Terminology Criteria for Adverse Events (CTCAE) will be utilized for AE reporting. CTCAE Version 5.0 is identified and located on the CTEP website at:

[http://ctep.cancer.gov/protocolDevelopment/electronic\\_applications/ctc.htm](http://ctep.cancer.gov/protocolDevelopment/electronic_applications/ctc.htm).

All appropriate treatment areas should have access to a copy of the CTCAE Version 5.0.

This study will be monitored by the Clinical Data Update System (CDUS). Cumulative CDUS data will be submitted quarterly to CTEP by electronic means. Reports are due January 31, April 30, July 31, and October 31.

### **7.1 Adverse Events and Potential Risks**

#### **7.1.1 Expected adverse events related to the procedure**

Pap smear collection, High Resolution Anoscopy (HRA) and anal biopsy.

Participants will likely experience pressure and urgency to defecate during the Pap smear collection and HRA. Anal bleeding may occur up to one week after the biopsy is taken.

The risk of infection is less than 1%.

#### **7.1.2 Expected adverse events related to imiquimod**

Most expected adverse events are local effects where the cream is applied. These include pain, burning, irritation, pruritus, erythema, edema, ulceration, bleeding, flaking and crusting of the skin, allergic reactions. Participants receiving imiquimod have also experienced headache, rash at other sites, back pain, pain/erythema/ulceration at adjacent sites (e.g. scrotum). Sinus infection, nausea, fever, and flu-like illness have also been reported.

#### **7.1.3 Expected adverse events related to topical 5-fluorouracil 5%**

Most expected adverse events are local effects where the cream is applied. These include pain, burning, irritation, pruritus, erythema, edema, ulceration, bleeding, flaking and crusting of the skin, allergic reactions. Scarring of treated areas has also been reported. Participants receiving 5-fluorouracil 5% have also experienced emotional upset, medicinal taste, thrombocytopenia, leukocytosis, hair loss, rash at other sites, pain/erythema/ulceration at sites adjacent to treated sites (e.g. scrotum), eye and nasal irritation, and herpes simplex reactivation. Women received 5-fluorouracil 5% have reported miscarriages, and one birth defect (ventriculoseptal defect) occurred in an infant born to a woman who was exposed to 5-fluorouracil 5% during pregnancy.

#### **7.1.4 Expected adverse events related to the study disease**

Anal HSIL may progress to anal carcinoma, whether observed or treated with study provided treatments. If suspected progression to SCC occurs, as outlined in [Section 5.5](#) of the protocol, the investigator may withdraw the participant from the randomized strategy and pursue treatment of anal HSIL or invasive cancer outside of the study as clinically indicated. If progression to SCC occurs, then the

participant must be withdrawn from the protocol and appropriate therapy instituted. Such participants should remain in study follow-up.

## **7.2 Classification of AEs by Severity and Relationship to Study Drug Administration**

- 7.2.1 Adverse Event: Any unfavorable and unintended sign (including an abnormal laboratory finding), symptom or disease temporally associated with the use of a medical treatment or procedure regardless of whether it is considered related to the medical treatment or procedure (attribution of unrelated, unlikely, possible, probable, or definite).
- 7.2.2 Life-threatening Adverse Event: Any AE that places the subject or subject, in view of the Investigator, at immediate risk of death from the reaction.
- 7.2.3 Serious Adverse Event (SAE): Any AE occurring at any dose that results in any of the following outcomes: Death, a life-threatening AE, inpatient hospitalization or prolongation of existing hospitalization, a persistent or significant disability/incapacity, or a congenital anomaly/birth defect.
- 7.2.4 Please note for hospitalization – All hospitalizations (or prolongation of existing hospitalization) for medical events equivalent to CTCAE Grade 3, 4, 5 must be reported regardless of the requirements for Phase of study, expected or unexpected, and attribution. For example, do not report an admission for pharmacokinetic sampling, but do report an admission for a myocardial infarction.
- 7.2.5 Toxicity: Toxicity is a term NOT clearly defined by regulatory organizations. Toxicity has been described as an AE that has an attribution of possibly, probably or definitely related to investigational treatment. To minimize confusion the NCI would recommend that the term toxicity NOT be utilized for AE reporting purposes. The CTCAE continues to use the term ‘toxicity’ because of familiarity.
- 7.2.6 Unexpected Adverse Event: Any AE that is not listed in available sources including the package insert, the Investigator’s Brochure, or the protocol.
- 7.2.7 Cancer Therapy Evaluation Program Adverse Event Reporting System (CTEP-AERS): An electronic system for expedited submission of AE reports.
- 7.2.8 Attribution: The determination of whether an AE is related to a medical treatment or procedure. Attribution categories:
  - Definite – The AE is clearly related to the investigational agent.
  - Probable – The AE is likely related to the investigational agent.
  - Possible – The AE may be related to the investigational agent.
  - Unlikely – The AE is doubtfully related to the investigational agent.
  - Unrelated – The AE is clearly NOT related to the investigational agent.

